714 location that is in close approximation to where the participants live. The exact CPD  
715 location will be determined with the help of the Chicago Park District liaison and will take  
716 into account safety of the participants and the location of where participants live. The  
717 Chicago Park District will only provide space for these visits and no Chicago Park  
718 District staff are involved in the research as recruiters, interventionists, asthma  
719 educators or to collect data.

720  
721 At each group session the following will occur:

- 722 1. Women will attend a 2 hour group session at the Chicago Park District or at  
723 UI Health/UIC. At the group session, participants will continue to receive  
724 asthma education (short videos and/or didactic session), watch a video on  
725 how to get started to walk and what barriers they may face. Participants will  
726 be asked to share their experiences engaging in physical activity with asthma.
- 727 2. Participant will be given an individualized step-goal not to exceed 3000 steps  
728 above their baseline calculated from accelerometer data over the entire  
729 course of the study.
- 730 3. Each participant will be given an ACTION participant manual (1st group  
731 session only).
- 732 4. Participants will be encouraged to walk during the group session for up to 15  
733 minutes. The interventionist and Chicago Park District liaison will identify safe  
734 locations for the women to walk at the group session site. Women will be able  
735 to walk at their own pace and stop at anytime. If the participant does not want  
736 to participate in the walking portion of the group visit they may opt-out by  
737 verbally telling the interventionist that they do not want to participate.
- 738 5. Participants will be asked to complete a session evaluation form. (Appendix  
739 9).
- 740 6. Participants will be given \$5 cash to assist with travel expenses incurred for  
741 each group visit.

742

743 At the last group session in the adoptive phase, the following procedures will occur and  
744 the participant will receive \$35 cash or gift card for this visit only:

745 :

- 746 1. Spirometry performed according to American Thoracic Society guidelines.  
747 Participants will be asked to wear nose clips and to take a deep breath in and  
748 blow their breath out as fast as they can into the spirometer. We will perform  

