749 repeated measurements (3 to 8 times) to ensure accuracy of results.
- 750 2. Weight
- 751 3. Incremental Shuttle Walk Test (ISWT) performed according to American  
752 Thoracic Society guidelines
- 753 4. Accelerometer distribution
- 754 5. Summative evaluation (visit 7 only; Appendix 10)

755

756 If a participant is not able to attend this session, we will contact the patient to scheduled  
757 an in person data collection visit at UI Health/UIC where the above procedures (#1-3)  
758 will be completed.

759

760 During or after Visit 7a is complete, participants will complete REDCap paper surveys (  
761 in person) or will be sent a link (email or text) to complete the following REDCap  
762 surveys electronically:

- 763 1. Physical activity questionnaires
- 764 2. Asthma Safety Measures
- 765 3. Asthma Control Questionnaire (ACQ)
- 766 4. Asthma-related quality of life questionnaire (AQLQ)
- 767 5. Adult Asthma Adherence Questionnaire (AAAQ)
- 768 6. PROMIS measures (Global Health, social roles satisfaction, mood, sleep)
- 769 7. Active Where Questionnaire
- 770 8. Self-efficacy for walking scale
- 771 9. Social support for exercise survey
- 772 10. Outcome expectation scale for exercise
- 773 11. Sleep Apnea Scale of the Sleep Disorders Questionnaire
- 774 12. Pittsburgh Sleep Quality Instrument

775 Key research personnel will send a reminder text, call and/or email (based on patient  
776 preference) up to 3 times the prior week to the group session stating “ACTION Asthma  
777 group will meet at X time and X place.”

778

779 Reminder messages will also be sent via phone, text or email (based on participant  
780 preference) up to 3 times per week to help them attain their weekly step goal (See  
781 Appendix 11 for sample text messaging).

782

783 An interventionist and/or [name] will attend the group sessions. Each group will  
784 last approximately 2 hours and may be audio-recorded to assess for intervention fidelity.  
785 If a participant declines audio-recording the session, then the session will not be  
786 recorded. The PI or co-investigator may then observe a group session intermittently to  
787 assess for intervention fidelity. If the session is recorded, the PI will review portions of  
788 the session. The sessions will be deleted once the pilot is complete. These audio  
789 recordings will not be transcribed. Patients will receive light snacks/refreshments at  
790 each session.

791

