792 If any of the group visits 3-7 are missed, the woman is asked to arrive 15 minutes early  
793 for the next meeting to receive an update. Her report will be emailed/phones/texted to her  
794 depending on her preference.

795

796 If a woman has missed several group visits and we have been unable to contact her, we  
797 will mail her a letter indicating to call us.

798

799 **Visit 7b: 24 week data collection (Enhanced Usual Care only)**

800 At Visit 7b the following procedures will take place at the Clinical Research Center at  
801 UIC:

- 802 1. Spirometry performed according to American Thoracic Society guidelines.  
803 Participants will be asked to wear nose clips and to take a deep breath in and  
804 blow their breath out as fast as they can into the spirometer. We will perform  
805 repeated measurements (3 to 8 times) to ensure accuracy of results.
- 806 2. Weight
- 807 3. Incremental Shuttle Walk Test (ISWT) performed according to American  
808 Thoracic Society guidelines
- 809 4. Accelerometer distribution
- 810 5. Physical activity questionnaires
- 811 6. Asthma Safety Measures
- 812 7. Asthma Control Questionnaire (ACQ)
- 813 8. Asthma-related quality of life questionnaire (AQLQ)
- 814 9. Adult Asthma Adherence Questionnaire (AAAQ)
- 815 10. PROMIS measures (Global Health, social roles satisfaction, mood, sleep)
- 816 11. Active Where Questionnaire
- 817 12. Self-efficacy for walking scale
- 818 13. Social support for exercise survey
- 819 14. Outcome expectation scale for exercise
- 820 15. Sleep Apnea Scale of the Sleep Disorders Questionnaire
- 821 16. Pittsburgh Sleep Quality Instrument

822

823 This visit will last approximately 2 hours and upon completion the participant will receive  
824 \$35 cash or gift card.

825

826 Participants will be given a postage paid envelope and be asked to mail the  
827 accelerometer back to study team after wearing it for 1 week. Reminder  
828 calls/texts/emails will be sent if we have not received the accelerometer within 2 weeks  
829 of completion of visit 7. If needed, a central location for drop-off of the accelerometer  
830 may be arranged with the participant.

831

832 **Maintenance Phase:** During the maintenance phase, participants will continue to  
833 receive reminder text messages to help them attain their weekly step goal no more than  
834 once a week.

835

836 **Visit 8: Post-maintenance booster session and data collection (12 weeks after**  

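### At week 24 the intervention arm is tested at a group session and controls at a stand-alone visit, and the replacement visit leaves out the accelerometer

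*Combined protocol and SAP*

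**What the plan says.** All of this is in Section 6.0 under Aim 3.

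- **Intervention arm, week 24 (Adoption phase).** The list introduced by "At the last group session in the adoptive phase, the following procedures will occur and" has five items: spirometry, weight, incremental shuttle walk test (ISWT), accelerometer distribution and a summative evaluation. Like every group session, this one lasts about 2 hours and has asthma education, a video and sharing of experiences. The session text adds: "Participants will be encouraged to walk during the group session for up to 15" minutes, at the woman's own pace and with the right to opt out.
- **Intervention questionnaires.** "During or after Visit 7a is complete, participants will complete REDCap paper surveys" in person, or receive an email or text link. Twelve instruments follow. No completion window is given.
- **Women who cannot attend that session.** They are contacted to arrange "an in person data collection visit at UI Health/UIC where the above procedures (#1-3", that is, items 1 to 3 of the five) are done.
- **Control arm, week 24 (Visit 7b).** "At Visit 7b the following procedures will take place at the Clinical Research Center at" UIC. Sixteen items follow: spirometry, weight, ISWT, accelerometer distribution and the same twelve questionnaires.
- **General rule (3 Data Collection Visits).** This text covers baseline, week 24 (Visit 7a/b) and week 36 for all participants. It lists the tests and questionnaires as done at these visits and says the accelerometer is provided at them.

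**The concern.** Aim 3 is meant to yield an efficacy estimate that can be used to power a later trial (Section 3.0). The week-24 contrast is useful for that only if both arms are measured in the same way.

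Here the setting of measurement follows arm. An intervention woman may have walked for up to 15 minutes shortly before spirometry or the ISWT. She may answer the scales on asthma control, quality of life, self-efficacy and social support straight after two hours of education and group discussion, or at some later date by link. A control woman meets none of this. These differences arise after randomisation, so randomisation does not balance them, and no analysis can separate them from the treatment effect.

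The replacement visit raises a different issue. If its item list is followed as written, week-24 accelerometer data are not collected from intervention women who miss the last session. Controls have no matching rule. The missing data would fall in one arm and depend on attendance, which is itself likely to be related to activity.

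**Working it through.** The plan states no figure on this point, so the check sets the texts side by side.

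**Which session is Visit 7a.** The rule "If any of the group visits 3-7 are missed, the woman is asked to arrive 15 minutes early" numbers the group visits 3 to 7. That makes five, matching the five adoption-phase sessions, so Visit 7a is the fifth and last.

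| Week 24 | Intervention, attends (7a) | Intervention, misses session | Control (7b) |
|---|---|---|---|
| Setting | Group session, about 2 hours | Separate data collection visit | Separate visit, about 2 hours |
| Site | UI Health/UIC or Chicago Park District | UI Health/UIC | Clinical Research Center |
| Spirometry, weight, ISWT | Yes | Yes (items 1-3) | Yes |
| Order relative to education and walking | Not stated | No group session | No group session |
| Accelerometer | Yes (item 4) | Not in items 1-3 | Yes (item 4) |
| 12 questionnaires | During or after, paper or link | Not made clear | Listed at the visit, mode not stated |

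**The accelerometer gap.** In both arms' lists the relevant line is "4. Accelerometer distribution". The replacement visit stops at item 3. The general rule supplies the accelerometer at the week-24 visit to all participants. The two texts cannot both be followed literally.

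**Which outcomes each issue can reach.**

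- Spirometry and ISWT: through recent exertion, if walking comes before testing.
- Questionnaires: through session content and through the time of completion.
- Accelerometer steps: these are recorded after the visit, so same-day context matters little. The exposure is the omission above.

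**Scale.** The size of any measurement shift cannot be computed from the documents. For comparison, assume the 80 women are split 1:1 with no dropout, which gives 40 per arm. The allocation ratio is not stated. The 95% half-width of a standardised mean difference is then 1.96 × √(2/40) = 1.96 × 0.2236 = 0.438 SD.

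**After maintenance.** Questionnaires are by REDCap survey with no split by arm. Testing is at the Chicago Park District for intervention women and at the Clinical Research Center for controls. Data collection is placed under Visit 8 together with the intervention-only booster, while the general rule and the control-group text call week 36 Visit 9. Testing on the booster day is therefore neither stated nor excluded.

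**The case against.** The strongest reply is that this is a feasibility pilot in a community setting chosen to be convenient for these women, with no sample size calculation (Section 11.0). Testing at a session they already attend is a reasonable choice. Both arms have the same instruments and the same standard: "Incremental Shuttle Walk Test (ISWT) performed according to American" Thoracic Society guidelines. Walking is optional and self-paced, and group sessions may be held at UI Health/UIC, so the site need not differ at week 24. Appendices 7 and 8 and Figure 2 are not visible and may settle some points. All of this stands as mitigation. It does not supply the order of walking and testing or a survey window. Whether the testing standard controls prior exertion cannot be seen here, and it does not govern questionnaires.

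On the replacement visit, the plan calls it a data collection visit, so the general rule may well be meant to cover it. Fitbit steps also continue in both arms. What stands is that the item list as written says otherwise. The accelerometer is also the device named for both the baseline and the post-intervention step counts, and Fitbits are issued only after baseline.

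A reader might infer that women who miss the session are also left without questionnaires. The text does not support that. The survey paragraph comes after the replacement-visit sentence, speaks of participants generally and allows a link. The attended session's own five items contain no surveys either. The fair statement is that their survey arrangements are not made clear.

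A reader might also infer that Visit 7a drifts away from week 24, given education at 1 to 6 weeks and sessions every 4 weeks. The gap before the opening group session is not stated, and week 24 is the nominal time for both 7a and 7b. Education at week 4, a 4-week gap and four 4-week intervals give 4 + 4 + 16 = 24, so the schedule can be consistent.

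**Conclusion.** Two things hold. First, the week-24 assessment conditions differ by arm, in session context and in stated questionnaire timing, so a measurement difference of unknown size and direction is possible. Second, the item list for the replacement visit conflicts with the general rule on accelerometers; read literally, it would make accelerometer steps missing in the intervention arm only, linked to attendance.

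It would go too far to say that the estimate is biased, or biased towards the intervention. Prior walking could help or hurt a test, and the documents give nothing to sign or size the effect. A difference in survey mode is possible but not shown, because the control mode is unstated. Nor is data loss shown, only a conflict of texts. No number of affected women can be given, since the plan states neither an attendance rate nor an allocation ratio.

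The half-width of about 0.44 SD rests on 40 women per arm with complete data. Against that imprecision, the case for change is that the difference is avoidable by wording and scheduling, not that it is known to be large. It is worth considering; it does not undermine the pilot. The Visit 8 and Visit 9 labels are a numbering matter to reconcile.

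**What to change.** 1. Extend the replacement visit from items 1-3 to include accelerometer distribution (item 4), and state that these women also receive the surveys, so that the Adoption phase text agrees with the general rule.
2. At Visit 7a, do the questionnaires, spirometry, weight and ISWT on arrival, before any group content or walking. In both arms, complete the questionnaires at the visit, as at baseline, with the same REDCap mode and one common window for any completed by link.
3. Record the actual assessment date, site and survey mode for every woman. If post-maintenance testing falls on the booster day, test before the booster. Reconcile the Visit 8 and Visit 9 labels, and report any remaining site difference as a limitation.

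**Cost.** Items 1 and 3 are wording and a few data fields. Item 2 means earlier or staggered arrival for intervention women at the last session. As a guide, the matching control list is planned at about 2 hours. The full set before a 2-hour session could make that day about 2 + 2 = 4 hours, less if some questionnaires go by link within the common window. Group size, staffing and equipment are not given, so the load on staff cannot be sized. If it proves too heavy, correcting the replacement-visit list, stating that tests come before walking and recording actual dates would still remove most of the ambiguity at little cost.

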### 893 **Aims 4 & 5 (Adapting Intervention Tools)**

894 We will recruit up to 15 AA women with asthma from our database of ~80 AA women  
895 with asthma that have given us permission to contact them for research studies. These  
896 women have already been identified as having asthma either through physician  
897 diagnosis and/or the use of a validated electronic health record (EHR) algorithm that  
898 identifies asthma patients with a high sensitivity and specificity (99% and 96%,  
899 respectively)[15, 16]. Potential participants will be contacted and asked screening  
900 questions to ensure they are still in our target age range of 18-70 years. Participants will  
901 be selected to ensure representation of age ranges. The sample size is determined by  
902 the theoretical saturation or the point when no new ideas relevant to the question are

903 obtained, which is generally 15[17].

904

905 Study Procedures for Aims 4 and 5:

906 1. Complete eligibility screening.

907 2. Securing informed consent.

908 3. Complete a brief demographic form. (Appendix 5)

909 4. Attend three 90 minute focus groups and provide perspective on issues such  
910 as video content, video scene selection and final video product.

911

912 Drs. [name] and a nurse interventionist will moderate all focus groups using an  
913 interview guide (Appendix 12) with semi-structured open-ended questions. The  
914 interview guide will be pre-tested for clarity, comprehension, and sensitivity and will  
915 provide sufficient flexibility to pursue unanticipated facets of topics that emerge in focus  
916 group discussions[4].

917

918 Each group will last approximately 90 minutes and be audio-recorded and subsequently  
919 transcribed. If one of the focus group members decline to be audio-recorded the  
920 session will not be audio-recorded and only field notes will be collected. Patients will  
921 complete written consent (1st session only), receive \$50 (cash) and light  
922 snacks/refreshments at each focus group.

923

924 The focus groups will take place in a private space at the University of Illinois at  
925 Chicago.

926

927 Key research personnel will send a reminder text and/or call the patient (based on  
928 patient preference) 24-48 hours prior to the focus group stating “ACTION asthma group  
929 will meet at X time and X place.”

930

### 931 **Aim 6 (Dissemination of study findings to study participants)**

932 We will disseminate our study findings and next steps to study participants by way of a  
933 newsletter. Using feedback from the CCTS Community Advisory Board we developed  
934 three newsletters to be disseminated to our study participants. The newsletters focus on  
935 thanking our participants, study findings, next steps and educational content related to  
936 physical activity and/or asthma. The newsletter will be sent on a monthly basis for 3  
937 months and will be disseminated by email, text or mail based on the preferred  
938 communication each participant indicated in the study. A pdf of the newsletters will be  
939 also available on [name] of Medicine Research Page.

940

## 941 **7.0 Expected Risks/Benefits**

942

943 The research involves minimal risk:

944  
945  
946  
947  
948  
949  
950  
951  
952  
953  
954  
955  
956  
957  
958  
959  
960  
961  
962  
963  
964  
965  
966  
967  
968  
969  
970  
971  
972  
973  
974

1. There is a chance that answering questions about their health may cause participants to become upset or distressed. If this should happen during a focus group or group session, the participant may take a break from the group or leave the group entirely.
2. Questionnaires: given that some questions ask personal information; it is possible that participants will be uncomfortable answering them. Participants will be explained they do not have to answer any question they are uncomfortable with.
3. There is also a chance for loss of privacy and loss of confidentiality in the unlikely event that unauthorized persons should see study data. Many protections will be taken to decrease the chances that this happens.
4. Spirometry (lung function test): risks associated with spirometry are minimal for most people. Because the test involves rapid and forced breathing, some people may experience temporary (lasting up to a few minutes) shortness of breath, lightheadedness and minor chest soreness. In rare cases, the participant may hyperventilate and become dizzy during spirometric testing. Any participant who feels faint should be guided onto the chair with her head down towards the knees, and encouraged to breathe slowly and deeply until she recovers. If the participant fails to recover normal breathing, faints, or reports feeling ill, the research assistant will summon the CRC nurse manager and physician immediately. The physician should always be consulted if there is any question regarding the participant's safety status during the exam.
5. Risk of pulmonary event: subjects will be asked to increase their daily physical activity and will perform up to 15 minutes of walking during the intervention group sessions, so there is the possibility of a pulmonary complication, such as an increase in respiratory symptoms (shortness of breath, cough, wheezing). We will minimize this risk by careful participant selection. Previous studies have shown the safety of increasing physical activity in sub-optimally controlled persistent asthma (Ma J et al. Ann Am Thorac Soc. 2015; 12(1): 1–11.)

975 Participants may have direct personal benefits from participating in the pre-pilot and  
976 pilot, as they will receive asthma education and learn how to best exercise with asthma.  
977 Further, participants may enjoy talking with other people about their experiences with  
978 asthma and physical activity. The participant's involvement will offer important  
979 information that will help refine and test the feasibility and acceptability of a physical  
980 activity program to improve the life of women with asthma.

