### 569 570 **3 Data Collection Visits: Baseline (week 0/Visit 1), post adoption phase (week** 571 **24/Visit 7a/b) and post maintenance phase (week 36/Visit 9) in all participants** 572 **(See appendix 8 for measures)**

573 At the data collection visits, the following procedures will take place at the Clinical  
574 Research Center at UIC or Chicago Park District location:

- 575 1. Secure informed consent (1st visit only).
- 576 2. Complete a brief demographic form.
- 577 3. Spirometry performed according to American Thoracic Society guidelines.  
578 Participants will be asked to wear nose clips and to take a deep breath in and  
579 blow their breath out as fast as they can into the spirometer. We will perform  
580 repeated measurements (3 to 8 times) to ensure accuracy of results.
- 581 4. Height and Weight
- 582 5. Incremental Shuttle Walk Test (ISWT) performed according to American  
583 Thoracic Society guidelines
- 584 6. Physical activity questionnaires

- 585 7. Asthma Safety Measures  
586 8. Asthma Control Questionnaire (ACQ)  
587 9. Asthma-related quality of life questionnaire (AQLQ)  
588 10. Adult Asthma Adherence Questionnaire (AAAQ)  
589 11. PROMIS measures (Global Health, social roles satisfaction, mood, sleep)  
590 12. Active Where Questionnaire  
591 13. Self-efficacy for walking scale  
592 14. Social support for exercise survey  
593 15. Outcome expectation scale for exercise  
594 16. Sleep Apnea Scale of the Sleep Disorders Questionnaire  
595 17. Pittsburgh Sleep Quality Instrument  
596 18. Neighborhood safety and social cohesion questionnaire  
597 19. Study randomization (1st visit only)  
598 20. Schedule asthma and physical activity (PA) education session with participant  
599 (1st visit only)  
600

601 Key research personnel will obtain consent in a private room in the Clinical  
602 Research Center. After consent is obtained, the other study procedures will be  
603 completed.  
604

605 This visit will last approximately 2 hours and upon completion the participant will  
606 receive \$35 cash or gift card. Patients will be offered light snacks/refreshments  
607 at this visit and given a visit summary sheet with their blood pressure, heart rate,  
608 weight, height, oxygen level, date of next study visit and a copy of spirometry  
609 results if desired.  
610

611 Participants will then be provided the following equipment at these data collection  
612 visits:

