837 **Visit 7) Booster session will only be for intervention group.**

838

839 At visit 8 booster session the following procedures will occur:

- 840 1. Attend a 2 hour group session at the Chicago Park District or at UI  
841 Health/UIC. At the group session, participants will review successes attained  
842 and barriers, lapses, and relapses encountered.
- 843 2. Participants will be asked to complete a session evaluation form. (Appendix 9).
- 844 3. Participants will be given \$5 cash to assist with travel expenses incurred for  
845 the group visit.

846

847 An interventionist and/or [name] will attend the group session. The group will last  
848 approximately 2 hours and may be digitally recorded to assess for intervention fidelity. If  
849 a participant declines audio-recording the session, then the session will not be  
850 recorded. The PI or co-investigator may then observe a group session intermittently to  
851 assess for intervention fidelity. If the session is recorded, the PI will review portions of  
852 the session. The session will be deleted once the pilot is complete. These audio  
853 recordings will not be transcribed. Patients will receive light snacks/refreshments at the  
854 session.

855

856 **Post-maintenance data collection (all participants)**

857 The following procedures will take place at the Chicago Park District (intervention  
858 group) or Clinical Research Center at UIC (enhanced usual care):

- 859 1. Spirometry performed according to American Thoracic Society guidelines.  
860 Participants will be asked to wear nose clips and to take a deep breath in and  
861 blow their breath out as fast as they can into the spirometer. We will perform  
862 repeated measurements (3 to 8 times) to ensure accuracy of results.

- 863 2. Weight  
864 3. Incremental Shuttle Walk Test (ISWT) performed according to American  
865 Thoracic Society guidelines  
866 4. Distribution of accelerometer  
867  
868

869 The following questionnaires will be completed by REDCap survey:

- 870 1. Physical activity questionnaires  
871 2. Asthma Safety Measures  
872 3. Asthma Control Questionnaire (ACQ)  
873 4. Asthma-related quality of life questionnaire (AQLQ)  
874 5. Adult Asthma Adherence Questionnaire (AAAQ)  
875 6. PROMIS measures (Global Health, social roles satisfaction, mood, sleep)  
876 7. Active Where Questionnaire  
877 8. Self-efficacy for walking scale  
878 9. Social support for exercise survey  

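### The one escalation step for a woman who faints or does not recover during spirometry relies on Clinical Research Center staff, but Aim 3 also places spirometry at Chicago Park District sites, where that step cannot be carried out as written

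*Combined protocol and SAP*

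**What the plan says.** **The response.** Section 7.0, item 4, lists the spirometry risks and then a sequence of responses. A woman who feels faint is dealt with on the spot: "Any participant who feels faint should be guided onto the chair with her head down towards the knees". If she goes on to faint, feels ill or does not regain normal breathing, the text escalates: "the research assistant will summon the CRC nurse manager and physician immediately". A general instruction closes the item: "The physician should always be consulted if there is any question regarding the participant's safety status during the exam".

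**The sites (section 6.0, Aim 3).**
- The general list of procedures for the three data-collection visits, which includes spirometry, gives two possible places, the CRC and a park: "Research Center at UIC or Chicago Park District location".
- Week 24, intervention arm: spirometry is done at the last adoption-phase group session, held at the Park District or at UI Health/UIC. A woman who misses it has a make-up visit at UI Health/UIC.
- Week 24, enhanced usual care arm: Visit 7b is at the CRC.
- Week 36: under Post-maintenance data collection, the line "The following procedures will take place at the Chicago Park District (intervention" sends one arm to a park, and its other half puts the enhanced usual care arm at the CRC. The description of the Enhanced Usual Care Group also has those women attending the CRC at weeks 24 and 36.

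**The park's role.** For the adoption-phase sessions the protocol limits it to premises: "Chicago Park District will only provide space for these visits and no Chicago Park". As that sentence goes on to make clear, the park's own employees take no part in the research.

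**The concern.** The protocol names its own spirometry risks and writes a response to them, but the escalation step is worded for one building. It fits the pre-pilot, where spirometry was done at Visit 1 in the CRC. Aim 3 adds park locations, and the step was not adapted to them. A research assistant at a park who follows section 7.0 literally would be told to summon a nurse manager who works elsewhere.

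What is at stake is whether a written safety instruction can be followed at a site that the same protocol prescribes. Aim 3 enrols women with sub-optimally controlled persistent asthma (ACT below 20), and each spirometry session involves 3 to 8 forced manoeuvres.

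**Working it through.** The plan gives no figure to reproduce, so the check is a side-by-side reading followed by a count of sessions.

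**Step 1. Is there another response for failed recovery or a faint?**
- The chair step in section 7.0 is not tied to a site, but it comes before the escalation and does not replace it.
- The closing sentence about consulting the physician names no place, but it gives no route for reaching a physician from outside the CRC. It may refer to the same physician as the sentence before it.
- Section 10.0 deals with reporting adverse events: a 24-hour study telephone number, sources of reports, and notification of the IRB, the NIH and the safety officer. It is not an on-site response.
- Section 4.2.b withholds spirometry after recent chest, abdominal or eye surgery. That narrows who is tested; it does not say what to do in an event.

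So one escalation step is stated, and it names CRC staff.

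**Step 2. Where is Aim 3 spirometry done?**

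| Visit | Intervention arm | Enhanced usual care arm |
|---|---|---|
| Baseline | CRC (sections 5.1 and 5.2); the general list in 6.0 also allows a park | the same |
| Week 24 | Park District or UI Health/UIC | CRC |
| Week 36 | Park District | CRC |

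The post-maintenance visit is set 12 weeks after Visit 7, and 24 + 12 = 36, so it is the week-36 visit although it is labelled both Visit 8 and Visit 9.

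**Step 3. How many sessions?** Inputs: 80 women (Aim 3); 1:1 allocation (assumed, as the ratio is not stated); no dropout.
- Intervention arm: 80 / 2 = 40 women.
- Week 36: 40 park sessions if the post-maintenance line is taken as written. The number is lower if the general CRC-or-park line also applies.
- Week 24: 0 to 40 park sessions, depending on where the last group session is held.
- Planned spirometry sessions in all: 80 × 3 = 240. Park sessions are then 40 / 240 = 17% if only week 36 is at a park, and (40 + 40) / 240 = 33% if week 24 is too.

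Baseline is not counted as park testing, because sections 5.1 and 5.2 place the first visit at the CRC. Sessions at UI Health/UIC outside the CRC are not counted either, because the text does not say whether CRC staff could be called from there.

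**The case against.** The best case on the other side is that this is an omission and a small one. Section 7.0 gives a step worded for the CRC, section 6.0 adds a site, and neither denies the other. The protocol describes the study as minimal risk, and most sessions are at the CRC in any case. That is fair as to size. It does not remove the problem: the post-maintenance text prescribes a site at which the stated step cannot be followed.

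The objection does defeat several stronger readings that a reader might infer.

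- **That the site difference biases a comparison between arms.** At week 36 site follows arm, so confounding of safety results may come to mind. But sections 9.0 and 11.0 specify no between-arm safety comparison. Adverse events reach the study through participants, families, providers and hospitals (section 10.0), not through CRC nurses. No event rate or mechanism is given by which stopped tests would differ by site.
- **That the minimal-risk statement depends on CRC cover.** Section 7.0 calls spirometry risks minimal for most people before it mentions any escalation, and it does not rest that on the CRC.
- **That nobody able to respond is present at the park.** The attendance line names an interventionist and/or one other person, but it describes the booster session. Post-maintenance data collection has its own heading and states no staffing. Section 7.0 assumes a research assistant, who does not appear in that line, so the line is not a full list for testing. The other attendee's name has been removed, so that person's profession is unknown.
- **That the shuttle walk is covered by the same gap.** The escalation step concerns spirometry only.

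**Conclusion.** The point holds as a gap between two sections. The only escalation step for a failed recovery, a faint or feeling ill during spirometry cannot be carried out as written at a Chicago Park District site. Section 6.0 allows such a site in general, makes it an option for the intervention arm at week 24, and prescribes it for that arm at week 36.

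Its extent is up to about 40 intervention-arm sessions at week 36 and 0 to 40 at week 24. This assumes 1:1 allocation and full retention, and for week 36 it takes the arm-specific line at its word. That line is supported by the two other statements that put controls at the CRC.

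The absence of a park version is judged on the visible text. The appendices are listed but not reproduced, and none has a title that suggests such a procedure. No claim is made about bias in an efficacy or safety comparison, about how often events would occur, or about who is in fact present at park testing.

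**What to change.** Reconcile section 7.0, item 4, with the parts of section 6.0 that place Aim 3 spirometry: the general data-collection list, the last adoption-phase session and post-maintenance data collection. The aim is that the stated spirometry response can be carried out at every site where spirometry is done. What the response contains, who is to be present or reachable, and which sites are used are for the sponsor to decide.

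The cost is a wording amendment. If the sponsor chooses to reconcile the sections by changing the site, some of the convenience of the park locations is lost for intervention-arm women at those visits. Any effect of extra travel on attendance in that arm should then be weighed. If the sponsor instead changes who attends, there may be a staffing cost, which the documents give no basis to estimate.
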